- 1) Diagnostic accuracy of UHR-CT using visual assessment of coronary artery disease is non-inferior to invasive, conventional coronary angiography for identifying vessels with hemodynamically significant CHD defined by an QFR-value of <0.8 in a vessel of 2.0 mm or larger in diameter.
- 2) Diagnostic accuracy of UHR-CT using quantitative assessment of coronary artery disease is non-inferior to invasive, conventional coronary angiography for identifying vessels with hemodynamically significant CHD defined by an FFR-value of <0.8 in a vessel of 2.0 mm or larger in diameter.

Lesion-Based Hypotheses

- 3) Diagnostic accuracy of UHR-CT using visual assessment of coronary artery disease is non-inferior to invasive, conventional coronary angiography for identifying lesions with hemodynamically significant CHD defined by an QFR-value of <0.8 in a vessel of 2.0 mm or larger in diameter.
- 4) Diagnostic accuracy of UHR-CT using quantitative assessment of coronary artery disease is non-inferior to invasive, conventional coronary angiography for identifying lesions with hemodynamically significant CHD defined by an QFR-value of <0.8 in a vessel of 2.0 mm or larger in diameter.

3. Background

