- I. . The presence of any other history or condition that the investigator feels would be problematic

6. Study Statistics

- a. Primary outcome variable**

The primary analysis will be a comparison of the diagnostic capability of the UHR-CT angiography to conventional coronary angiography at the patient level with the reference standard being quantitative flow reserve (QFR). A positive patient will be defined as having at least one vessel with a flow reserve <0.8 .

b. Secondary outcome variables

A secondary analysis will be performed at the vessel level. Similar to the primary analysis, a comparison of the diagnostic capability of UHR-CT angiography and conventional coronary angiography will be performed. A positive vessel will be defined as having at least stenosis with a flow reserve <0.8 . In addition, study groups will be compared for occurrence of adverse effects, radiation doses, contrast volume, and costs.

c. Statistical Plan including sample size justification and interim data analysis

In order to assess the diagnostic accuracy of UHR-CT angiography compared with invasive angiography to flow reserve we will consider the result from CT angiography as continuous measures on a patient, vessel, and segment level. The analysis will be based on the area under the receiver operating characteristic (ROC) curve (AUC). The gold standard will be coronary flow reserve estimations by either FFR, iFR, or QFR. Construction of the ROC curves using the CT and ICA measures will be based on the well-known result that the curve based on the risk score has the same ROC curve as the optimal curve based on the likelihood ratio (Pepe, 2003, Result 9.4). The risk score will be estimated by logistic regression analysis with CT angiography and ICA as independent predictor variables. The resulting risk score (the linear predictor from the logistic regression) will be used to construct the ROC curve. The AUC and its standard error will be estimated nonparametrically using standard methods (Pepe, 2003).

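### The plan does not say how within-patient correlation is handled for vessel-, lesion- and segment-level AUCs; ordinary standard errors there would most likely give intervals that are too narrow

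*Combined protocol and SAP*

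**What the plan says.** Section 6c takes the CT result as "continuous measures on a patient, vessel, and segment level". The ROC curve is built from a fitted score: "The risk score will be estimated by logistic regression analysis with CT angiography and ICA as independent predictor variables". The variance is then covered in one sentence for all levels: "The AUC and its standard error will be estimated nonparametrically using standard methods (Pepe, 2003". The sample size paragraph adds a 95% confidence interval and a 6% non-inferiority margin, without saying to which level of analysis they apply.

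The primary analysis in Section 6a is a "comparison of the diagnostic capability of the UHR-CT angiography to conventional coronary angiography at the patient level". Section 6b adds: "A secondary analysis will be performed at the vessel level". Section 2 lists vessel- and segment-based accuracy as secondary objectives and words the vessel hypotheses as inferential claims, that UHR-CT is "non-inferior to invasive, conventional coronary angiography for identifying vessels with hemodynamically significant CHD defined by an QFR-value of <0.8". Two hypotheses are stated for vessels and two, in the same form, for lesions. Section 6c does not name lesions as a unit of analysis.

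Clustering, within-patient correlation, robust variance, mixed models, GEE and patient-level resampling appear nowhere in the document.

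**The concern.** The ordinary nonparametric variance of an empirical AUC assumes independent units. Vessels and segments of one patient are not independent. They share one scan, one heart rate and one exposure window, with tube settings adjusted to that patient's scout noise (Section 4, UHR-CT protocol). They also share a calcium and stent burden, which Section 3 names as the source of CT error and on which Section 5 selects patients. Disease itself tends to cluster within patients.

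If the single rule is applied as it reads, the stated precision below patient level will probably be too good. In a non-inferiority comparison this works in the favourable direction: a standard error that is too small lifts the lower limit and makes the margin easier to clear.

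**Working it through.** **The plan's own figure.** 180 / (1 − 0.10) = 200, which matches. It is a patient-level number with one record per patient, so clustering of vessels does not enter it. The document gives no standard error, design effect or sample size below patient level, so there is nothing further to reproduce.

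**Why correlation matters.** Let d be the CT-minus-ICA difference in placement value for each of m positive units, and f the same for each of n negative units.

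- Ordinary variance: var(d)/m + var(f)/n.
- Clustered variance: sum the centred d/m and f/n within each patient, square the sums, and add over patients.

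The two differ by cross-products between units of the same patient. A shared reading error pushes two units of the same disease status the same way, which adds variance. It pushes two units of opposite status in opposite ways, which removes variance. The ordinary standard error is therefore too small when reading errors are shared and disease clusters, so that same-status pairs predominate.

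**Inputs from the plan:** 180 evaluable patients; AUC 0.83 for CT and 0.77 for ICA (Section 6c).

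**Assumed, because the plan gives none:** 3 vessels or 12 segments per patient; binormal scores; within-patient correlation of disease and of reading error as shown. The second table also assumes 30% of vessels and 12% of segments positive, and a CT-ICA error correlation of 0.5.

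**Results for the CT-minus-ICA difference** (ratio = true SE / ordinary SE; coverage of the ordinary nominal 95% interval).

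Equal disease and error correlations:

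| Correlation | 3 vessels: ratio, coverage | 12 segments: ratio, coverage |
|---|---|---|
| 0.2 | 1.04, 93.5% | 1.08, 93.6% |
| 0.4 | 1.07, 93.1% | 1.42, 82.9% |
| 0.6 | 1.20, 90.1% | 1.66, 76.2% |

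Correlations varied separately:

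| Disease, error | 3 vessels: ratio, coverage | 12 segments: ratio, coverage |
|---|---|---|
| 0.2, 0.3 | 1.04, 93.9% | 1.16, 91.1% |
| 0.5, 0.3 | 1.08, 92.4% | 1.36, 85.7% |
| 0.5, 0.5 | 1.15, 91.2% | 1.49, 80.1% |

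**Consistency check.** Expected coverage at ratio r is 2Φ(1.96/r) − 1. For r = 1.20, 1.96/1.20 = 1.633, giving 89.8%. For r = 1.66, 1.96/1.66 = 1.181, giving 76.2%. Both agree with the first table. A repeat of that table's settings at 30% and 12% prevalence agreed with its ratios to within 0.1. It showed no measurable shortfall for vessels at correlation 0.2, so that row should be read as little or no effect.

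**Effect on the lower limit** (disease and error correlation both 0.5).

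- Vessels: the ordinary SE is 0.0216 and the true SE 0.0247, so the limit sits 1.96 × 0.0031 = 0.006 too high.
- Segments: 0.0152 against 0.0226, so 1.96 × 0.0074 = 0.015 too high.

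**Where the effect disappears or reverses.** With reading errors uncorrelated within patient, the ratio was 0.96-1.03. With exactly one positive vessel of three in every patient it was 0.82-0.90 (coverage 97-98.5%), so the ordinary interval was too wide.

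**Does a clustered variance cure it?** The patient-clustered SE gave coverage of about 92-96% across the settings.

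**Not covered.** Lesions were not simulated, because the plan gives no number of lesions per patient. The simulations also use the scores directly and do not reproduce the logistic fitting step.

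**The case against.** A reader might infer that the plan treats vessels of one patient as independent. It does not say so. It names no variance formula and no independence assumption; a clustered variance and a patient bootstrap are both nonparametric; and what the cited textbook covers cannot be checked from the document. This objection stands: the fault is an unqualified rule and silence on clustering, not a stated error.

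A reader might also infer that the intervals are certain to be too narrow. The uncorrelated-error case and the one-positive-vessel case show otherwise. The second cannot hold throughout this trial, since a patient-level AUC needs patients with no positive vessel, and Section 9 lists three-vessel disease among possible findings. The first is unlikely given the shared scan and calcium burden. Too narrow is therefore the likely direction, but no more than likely.

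The size can be challenged as well. Every correlation is assumed. The vessel effect is modest, and vessel level is the only level below patient that Section 6b lists. The largest effects are for segments, where Section 2 sets an objective but no hypothesis. The 6% margin is never expressly assigned below patient level. All of this stands and limits the weight of the point.

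Finally, it would be wrong to infer that the trial's main conclusion or its size is in doubt, because the primary comparison has one record per patient.

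**Conclusion.** The concern holds in a limited form. One unqualified standard-error rule covers patient-, vessel- and segment-level AUCs, and nothing in the plan accounts for several units per patient. If the ordinary independent-unit standard error is used, secondary intervals will most likely be too narrow, including those for the four vessel- and lesion-level non-inferiority hypotheses. The shortfall is modest for vessels and potentially serious for segments; the lesion-level size is unknown. The ranges are illustrative: they rest on the assumed unit counts, prevalences and correlations, and the effect nearly vanishes if reading errors are uncorrelated within patient.

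The change should be made, since non-inferiority claims are planned at these levels and the variance method should not be left to be chosen after the data are seen.

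**What to change.** Add to Section 6c: for all vessel-, lesion- and segment-level analyses, the variance of each AUC and of the paired CT-ICA difference will be estimated either with a patient-clustered nonparametric ROC method (Obuchowski) or with a bootstrap that resamples whole patients and refits the logistic risk score in each resample. State which of the two is the main method. Keep the ordinary paired nonparametric method for the patient level.

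The cost is one sentence and available methods, with no new data and no change in sample size. Secondary intervals become wider, slightly for vessels and possibly noticeably for segments. If within-patient correlation turns out to be negligible, they will barely change.

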If the patient appears to be eligible for the study based on the initial evaluation, informed consent will be obtained. To reduce in person activities, baseline information and medical history will be collected via telephone call. Blood will be obtained at the time of CTA (during IV placement) for laboratory testing of serum creatinine.

The clinically indicated coronary angiogram will not be delayed to complete the research protocol. If the CTA scan cannot be scheduled prior to the clinically indicated coronary angiogram the patient will not be enrolled in the trial. Consented patients will continue to be evaluated for participation in the trial through the imaging period.

Imaging Period

The imaging period will consist of two tests: 1) ultra-high-resolution CT (UHR-CT) angiography; 2) conventional coronary angiography (CCA). All enrolled patients referred for a clinically indicated catheterization will first receive a UHR-CT angiogram to avoid conflict with coronary artery revascularization.

UHR-CT Imaging

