Images will be prospectively triggered using ECG gating which reduces radiation exposure to the patient compared to retrospective gating. Tube voltage and current will be adjusted according to image noise characteristics during scout imaging. A tube setting of 120 kV with 580 mA will be required for most patients in the setting of severe calcification and/or stenting. Target exposure will be 70-80% of the R-R cycle for heart rate ≤ 60 bpm. Heart rate of 61-70 will require a widened exposure window of 65-85% of the R-R cycle. Gantry rotation will be 350 ms with a 160 x 0.25 mm collimation in super high resolution mode, requiring approximately 6.5 second scan time. The estimated range of radiation dose for CT coronary angiography will be 4.3-10.7 mSv depending on patient size and weight.

Total estimated radiation dose, including calcium scoring, and CT coronary angiography, will therefore range between 4.8-12.7 mSv. For comparison, a standard nuclear stress test typically results in a radiation dose of 10-12 mSv to the patient (Einstein A, Circulation 2007). Diagnostic cardiac catheterization for conventional coronary angiography typically averages 12 mSv radiation dose (Rochitte et al., Eur Heart J 2014).

A copy of the anonymized raw data (without any patient identifiers) will be forwarded to the CT Core Laboratory for analysis within 1 week of the scan. CT raw data and reconstructed data will be saved by the site for at least 5 years after completion of the study.

Within 3 weeks of the CTA, the CTA will be reviewed for non-cardiac findings by a locally qualified, institutionally approved radiologist, and reported. The investigator will report these findings to the patient's clinical physician and patient in a timely fashion preferably prior to or during the 30-day follow-up.

A pre-catheterization serum creatinine should be obtained post CTA (per local standard, or preferably > 2 days post CTA).

Conventional Coronary Angiography

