Patients will undergo their clinically indicated cardiac catheterization/coronary angiography, within 60 days of CT imaging with a recommended goal of completing all imaging within 30 days. A time window of ≥ 24 -48 hours is recommended between CT imaging and conventional coronary angiography to minimize cumulative risk of contrast exposure from these two tests. Coronary angiography will be performed according to general standards to obtain optimum angles. Isocenter calibration must be performed for all studies to enable quantitative flow reserve (QFR) assessment. Intracoronary nitroglycerine will be administered (150-200 mcg) prior to first image of the left coronary artery system and right coronary artery. This is to standardize the vasomotor state of the coronary artery and eliminate any potential for catheter-induced changes (i.e., catheter induced spasm).

Fractional-flow-reserve (FFR) assessment may be performed as clinically indicated but not solely for research purposes. Coronary angiographic images will be saved in the universal DICOM format and forwarded to the Angiographic Core Laboratory for Quantitative Coronary Angiographic Analysis. Quantitative coronary analysis (QCA) will be performed using standard, validated analysis software from Medis Medical Systems (Medis QCA). QFR will be performed using a dedicated software (QFR, Medis Medical Imaging Systems).

A post-catheterization serum creatinine should be obtained per local standard, or preferably within 48-72h post invasive coronary angiogram.

Data Sharing

The data acquired for this study are owned by the study funder, Canon Medical Systems. Data sharing will require authorization by the study sponsor. The sponsor may use results and data from this study for researching, developing products or equipment, software for such product or equipment, or its enhancements or upgrades and in clinical application training. JHU shall remove any confidential information about a patient, including, without limitation, the patient's identity or other information which JHU is obligated to maintain as

Date: March 4, 2025
Principal Investigator: [name]
Application Number: IRB00209321

confidential under applicable laws, from the reports and images before providing these to the sponsor.

[figure not shown]
Follow-Up Period

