Patients with known allergic reactions to CT contrast or to iodine will be excluded from participation. At least 1 investigator (Physician) will be present during the study in the case of the need to treat a previously unknown contrast allergy and during saline infusion to monitor for adverse reactions. Patients with a reduced glomerular filtration rate (<60) or history of contrast induced nephropathy will be excluded. All patients will be required to have a minimum of 24 hours (recommended at least 48 hours) between their CTA scan and any other procedure requiring iodinated contrast administration, i.e., cardiac catheterization. All patients will have a creatinine repeated prior to their cardiac catheterization. A follow-up creatinine is strongly recommended within 72 hours after catheterization procedure. Patients will be hydrated with normal saline prior to and following their CTA scan. Menstruating women must have a negative pregnancy test within 24 hours of CTA and angiographic imaging. Pregnant women are excluded. Women of childbearing age will have a lead apron placed over their abdomen and pelvis in order to reduce the radiation exposure to the ovaries. Prospective scan triggering will be applied to all patients to reduce radiation dose compared to retrospective gating.

Intravenous catheters will be inserted by a nurse/technician who is well trained in that procedure.

All patients will be carefully screened for the presence of any contraindications prior to them signing the consent form.

It is recommended that nitroglycerin will **not** be administered to subjects who have used phosphodiesterase V inhibitors in the past 72h, i.e., treatment for erectile dysfunction. It is recommended that NSAIDS will be held prior to contrast media administration.

c. Plan for reporting adverse events unanticipated problems or study deviations.

Notification of events occurring within 30 days of study enrollment (CTA imaging) will be transmitted within 24 hours of occurrence electronically to the Study Coordinator and Johns Hopkins Hospital respectively. Safety monitoring of the study will be performed by the study team biannually. A data and safety monitoring board (DSMB) will be appointed for specifically monitoring the safety of participants and data. The DSMB will be outside JHU.

d. Legal risks such as the risks that would be associated with breach of confidentiality.

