Individual patient medical information obtained as a result of this study it is considered confidential. The patient will be identified by an assigned unique identifier code (number and letter code), that will be used on all films/study binders. The data will be stored in a secure area. The principal investigator/study coordinator will maintain documents that identify the patient in strict confidence, except to the extent necessary to allow auditing by the JCCI and FDA. No participants in the study will be identified by name in any report, publication, or presentation of this study or its results. Confidentiality will be maintained by removing all identifying information from films prior to their being transmitted and read by the independent core labs. No genetic testing will be performed.

9. Benefits

Individual participant

We expect no direct benefit to patients participating in this study. All patients will receive a CTA examination of the heart at no cost. All CTA examinations will be reviewed locally by a cardiologist and radiologist. Alert incidental findings that need further medical follow-up will be communicated to the patient's treating physician within 7-14 days of procedures. Alert incidental findings include, but are not limited to: pulmonary emboli, aortic dissection, pulmonary masses, three vessel coronary disease, left main coronary disease.

Society

Date: March 4, 2025
Principal Investigator: [name]
Application Number: IRB00209321

This research will benefit society by helping healthcare professionals to evaluate this new technology which has the potential to become a routine non-invasive diagnostic tool for evaluation of coronary artery disease.

10. Payment and Remuneration

Patients will not be compensated for their participation in the study. Patients will receive a parking coupon (\$20 value) to cover parking expenses at the Johns Hopkins Hospital. If a patient requires alternate transportation, the patient will receive reimbursement for the cost of the transportation in lieu of the parking coupon. Participants will also receive \$100 upon completion of the CT scan and an additional \$150 for completing the CT coronary angiogram (total of \$250 for both scans).

11. Costs

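### Counted from the CTA, the non-cardiac read is permitted up to 7 days after the 14-day limit for reporting alert findings

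*Combined protocol and SAP*

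**What the plan says.** Two parts of the combined protocol and SAP set times for findings on the CTA.

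**Section 4, UHR-CT Protocol for Coronary Angiography.** The local non-cardiac read has this limit: "Within 3 weeks of the CTA, the CTA will be reviewed for non-cardiac findings by a locally qualified, institutionally approved radiologist, and reported". The investigator then passes the findings to the patient and the clinical physician "in a timely fashion preferably prior to or during the 30-day follow-up". This part does not distinguish alert findings from others and does not refer to Section 9.

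**Section 9, Benefits, Individual participant.** All CTA examinations get a local review by a cardiologist and a radiologist, with no time given. The next sentence sets the alert limit: "Alert incidental findings that need further medical follow-up will be communicated to the patient's treating physician within 7-14 days of procedures". The list that follows mixes non-cardiac and coronary findings: "Alert incidental findings include, but are not limited to: pulmonary emboli, aortic dissection, pulmonary masses, three vessel coronary disease, left main coronary disease". Which procedure starts the clock is not defined.

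The order of the two tests matters for that clock. Under Imaging Period in Section 4, "All enrolled patients referred for a clinically indicated catheterization will first receive a UHR-CT angiogram to avoid conflict with coronary artery revascularization". Catheterization follows "within 60 days of CT imaging with a recommended goal of completing all imaging within 30 days" (Conventional Coronary Angiography). Section 8b sets the shortest gap: "All patients will be required to have a minimum of 24 hours (recommended at least 48 hours) between their CTA scan" and any other procedure that uses iodinated contrast.

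**The concern.** Three of the five listed alerts (pulmonary emboli, aortic dissection and pulmonary masses) are what a non-cardiac read is meant to detect. A site learns of them only when someone reads the scan. If the read may come after the date by which an alert must have reached the treating physician, a site can follow Section 4 exactly and still break Section 9.

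What is at stake is a permitted delay in passing on a serious finding. Section 4c blinds treating clinicians to a CTA done solely for research, so for such a scan they depend on the local review to be told. The sites also work from one protocol under separate ethics approvals, and the coordinating center has to assure compliance. Two time limits that do not refer to each other make it unclear when an alert counts as late.

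**Working it through.** The plan gives no figure of its own to reproduce. The check is date arithmetic on its stated limits.

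**Inputs**
- Latest permitted non-cardiac read: 3 weeks = 3 × 7 = 21 days after the CTA (Section 4, UHR-CT Protocol).
- Outer alert limit: 14 days (Section 9).
- Day of catheterization after the CTA, C: at least 1 (24 hours, Section 8b), at most 60 (Section 4, Conventional Coronary Angiography).
- The 30-day follow-up: 30 days after catheterization (Section 4, Follow-Up Period).

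**Step 1. Clock starts at the CTA.** For a read on day r, the alert is at least r − 14 days late.
- r = 14: 14 − 14 = 0 days.
- r = 15: 15 − 14 = 1 day.
- r = 21: 21 − 14 = 7 days.

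Reads on days 15 to 21 therefore comply with Section 4 and miss the Section 9 limit by 1 to 7 days. This assumes that the alert goes out on the day of the read; any reporting time adds to the delay.

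**Step 2. Clock starts at catheterization.** The limit falls on day C + 14 after the CTA, so a day-21 read is late by 21 − (C + 14) = 7 − C days.
- C = 1: 6 days late.
- C = 2: 5 days late.
- C = 6: 1 day late.
- C = 7: 0 days; no conflict from here on.

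On this reading the conflict is confined to catheterization on days 1 to 6.

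**Step 3. The 30-day preference.** The follow-up falls on day C + 30 after the CTA, at the earliest 1 + 30 = day 31. That is 31 − 14 = 17 days past the alert limit on the CTA clock, and 30 − 14 = 16 days past it on the catheterization clock. The preference cannot serve as the target for alerts on either clock.

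**Step 4. What read date would fit.** On the CTA clock the read must be done by day 14 at the latest, which leaves 14 − 14 = 0 days to report. A read by day 7 leaves 14 − 7 = 7 days.

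**The case against.** The strongest reply is that the two rules are both maxima and do not contradict each other. Section 4 covers all non-cardiac findings, Section 9 sets a tighter limit for a named subset, and the specific rule governs. A site that applies both can comply by reading early. This stands, and a reader who infers that the rules cannot both be met goes too far. What remains is that Section 4 expressly permits a read on a date that makes the alert limit unattainable on the CTA clock, and does not point to Section 9.

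A second reply is that Section 9 attaches the alert limit to its own local cardiologist and radiologist review. That review may be separate from the three-week read and may catch an alert sooner. This also stands. A reader might infer that a late non-cardiac read would leave an alert undetected with no other safeguard; the documents do not support that, because this review exists. But it has no date, so it does not guarantee a read by day 14.

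A third reply concerns the clock. Section 9 does name a start, *procedures*, in a paragraph about CTA examinations, so the CTA is the natural reading. A reader might infer that the plan lets an alert wait until after a late catheterization. That rests on the less natural reading, on which the conflict also largely disappears (Step 2). The term is undefined and worth fixing, but it should not be used to enlarge the problem.

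Finally, 14 days may itself seem slow for an embolus or a dissection. The documents give no basis for another limit. This point asks only that the read fit the limit already chosen.

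**Conclusion.** The inconsistency is real and minor. Counted from the CTA, the permitted read can fall up to 7 days after the alert limit. The result rests on three assumptions: the clock starts at the CTA, the 14-day outer end of the range is the limit, and no alert is sent before the scan is read.

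The 7 days compare two outer limits. They do not show that any alert was or will be late. The documents do not say when reads are actually done or how often alerts occur, so the number of patients affected cannot be derived, and the share of permitted read days after day 14 should not be taken for it.

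A reader might also infer a bias in the accuracy comparison. The documents do not support that from this point: readers of the CTA, ICA and QFR images are blinded to the other imaging (Section 4c), and the timing of a non-cardiac read enters no analysis in Section 6. The coronary alerts, left main and three-vessel disease, do not depend on the non-cardiac read and are outside this point.

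**What to change.** Three changes of wording:

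1. In Section 4, UHR-CT Protocol for Coronary Angiography, require the non-cardiac read early enough to meet the alert limit. It must come before day 14 after the CTA, for example within 7 days, which leaves 7 days to report. The 7 days are a suggestion; any date that leaves time to report by day 14 would do.
2. In the same place, state that alert findings follow the Section 9 limit and not the 30-day follow-up preference.
3. In Section 9, replace *of procedures* with *of the CTA*.

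The cost is an earlier deadline for a read that is already required. With a 7-day limit it is due up to 21 − 7 = 14 days sooner than now allowed. No scan, visit or additional read is needed, and sites already have a one-week task for each scan, sending the anonymized raw data to the CT core laboratory.

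The change helps only scans still to come. The document is dated March 2025, multi-center enrollment was expected to start in summer 2022 and run 18 to 24 months, and Section 6d allows it to be extended, so how many scans remain is not known. A 7-day limit also does not ensure a read before a catheterization done in the first week.
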